STATISTICAL ANALYSIS PLAN FOR
“Seasonal Differences in Home Dialysis Uptake and Initiating Dialysis in the Hospital”

PROTOCOL ID: HS-18-00530-2

SECONDARY ID: K08DK118213

Version #1

Last Modified: 6/8/2021

PI: [name], MS

Keck School of Medicine of the University of Southern California

Cohort construction

- 1) Identify incident adults who started dialysis from 12/1/2007 – 11/30/2017
 - a. USA, no transplant or death in first 90 days, dialysis first modality
 - b. Has medical evidence form
 - c. Has Medicare AB 30 days prior to first date of dialysis
- 2) Create season/year variables based on the first date of dialysis
 - a. Season is winter, spring, summer, fall
 - b. For December, use the following year (i.e., we want 12/2012-2/2013 to be “winter of 2013”)
- 3) Outcomes:
 - a. Type of dialysis at start (home versus in-center), end of month 3, 6, 9, 12
 - i. Indicator for whether patient is alive by end of month 3, 6, 9, 12
 - b. Time until home dialysis
 - i. Indicator for whether patient used home dialysis
 - ii. Censor for transplant, death, day 360, or end of follow-up, whichever occurs soonest
 - c. Whether the patient had a hospitalization in the 14 days prior to first_se (include if first_se occurs during the hospitalization)
 - i. Categorize the hospitalization as acute infectious respiratory OR one of the following cardiac (myocardial infarction, stroke/TIA, arrhythmia, fluid overload) if either of the following is true:
 1. Any of the diagnosis codes has one of the following CCS: 1, 2, 3, 7, 97, 100, 108, 109, 112, 122, 123, 125, 131
 2. The principal diagnosis code is one of the following CCS: 101, 105, 106, 107, 129
 3. (We use CCS categories as constructed by AHRQ)
 - ii. Otherwise, the hospitalization is non-acute cardiac/infectious-respiratory
- 4) Covariates
 - a. Patient level
 - i. Age
 - ii. Sex
 - iii. Race
 - iv. Ethnicity
 - v. Whether patient is dual eligible
 - vi. Employment status
 - vii. Type of dialysis access at the start of dialysis
 - viii. Whether patient had a nephrologist prior to dialysis start
 - ix. Primary reason for ESRD
 - x. Comorbidities using the CMS 2728 Form
 - b. Facility characteristics
 - i. Profit status
 - ii. Chain vs. independent
 - iii. Size of facility (Number of patients)
 - iv. Staff : patient ratio
 - v. ESRD Network
 - c. Zipcode Characteristics

- i. Median income
 - ii. High school graduation rate
 - iii. % below poverty
 - d. Yearly level fixed effects (an indicator for each year as defined above)
- 5) Using multiple imputation (chained equations and ordinal logit) to impute missing characteristics. We use ordinal logit because all variables (including continuous ones) will be modeled as categorical variables.
 - a. Variables used for imputation: Covariates as above, type of dialysis at start, whether the patient had an acute cardiac/infectious-respiratory, or other hospitalization within 14 days of dialysis
 - b. 10 imputations
 - c. Recombine estimates using Rubin's rules

PLANNED ANALYSES

Table 1: Descriptive statistics (frequencies and percentages) of all covariates, stratified by season of dialysis start

Table 2: Descriptive statistics (frequencies and percentages) of each hospitalization type by season of year. Compute the ratio in frequency between winter and summer

Figure 1: Unadjusted seasonal differences in home dialysis and # of patients starting with a hospitalization

- A) Y axis: # of in-center patients, X axis: time; series: show patients who start with a hospitalization and patients who start without a hospitalization
- B) Y axis: # of home patients, X axis: time; series: show patients who start with a hospitalization and patients who start without a hospitalization
- C) Compute log rank test (p-value)

Figure 2: Differences in time to home dialysis uptake by season and by whether patients start with a hospitalization

- Kaplan-Meier curves, censoring for death, transplant, loss to follow-up (1 year maximum follow-up)
- A) By season of year
- B) By whether patients start with and without a hospitalization
- C) Compute log rank test (p-value) for A & B

Figure 3: Mortality by season of year

- Kaplan-Meier survival curves, censoring for loss to follow-up
- By season of year
- Compute log rank test (p-value)

Regressions (using multiple imputation). Robust standard errors for all models.

- A) Logits (each outcome is a different regression)
 - a. Outcome: home dialysis at start, months 3, 6, 9, 12
 - b. Exposure: season of year, whether hospitalized (and type of hospitalization)

- c. Covariates: as above
- B) Cox
 - a. Outcome: time to home dialysis (st set data)
 - b. Exposure: season of year, whether hospitalized (and type of hospitalization)
 - c. Covariates: as above
- C) Subgroup analyses
 - a. Repeat A and B but interact the exposures
 - b. For each of the subgroups, compute the following:
 - i. winter + winter##hospitalized
 - ii. hospitalized + winter##hospitalized
 - iii. Repeat for spring, fall
- D) Planned Sensitivity Analyses
 - a. Complete Case Analysis

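### The model for home dialysis at start adjusts for access type at start, which for peritoneal dialysis patients follows from the outcome

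*SAP*

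**What the plan says.** - **Covariate.** Cohort construction, item 4(a)(vii), lists "Type of dialysis access at the start of dialysis". No levels are given, and nothing says what is recorded for a patient without vascular access.
- **Outcome.** Item 3(a) defines "Type of dialysis at start (home versus in-center), end of month 3, 6, 9, 12". Regressions A(a) turns this into five logits: "Outcome: home dialysis at start, months 3, 6, 9, 12".
- **Model.** Regressions A(c) refers back to the full covariate list with no exception for any outcome. The exposures in A(b) are season and hospitalization with its type. C(a) extends the same specification: "Repeat A and B but interact the exposures".
- **Missing data.** The imputation model in item 5(a) uses "Covariates as above, type of dialysis at start" together with hospitalization.
- **Sensitivity.** Section D lists one analysis: "Complete Case Analysis". No adjusted model without access is planned anywhere.

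**The concern.** In the at-start logit, covariate and outcome are fixed at the same moment. Home hemodialysis uses the same kinds of vascular access as in-center dialysis, so for those patients access can vary within modality. A peritoneal patient's access is determined by the modality. For these patients the covariate restates the outcome and cannot be a confounder.

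Each plausible coding has a problem:

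1. **A peritoneal level.** It predicts home dialysis perfectly or nearly so. Either its patients are dropped or its coefficient is unbounded or extreme. The exposure odds ratios then compare home hemodialysis with in-center dialysis, which is narrower than the home uptake named in the SAP title.
2. **Vascular levels only.** Peritoneal patients have no applicable value. If that is treated as missing, item 5 imputes a vascular access that never existed, borrowing from home hemodialysis patients. The complete-case analysis would instead lose the peritoneal patients, so the one planned sensitivity analysis cannot reveal the fault.
3. **Collapsed levels**, such as central catheter versus all other. The model fits without warning, but peritoneal starters are counted as non-catheter, so the model still conditions on a consequence of the outcome.

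At stake is the first of the five logits and its interaction version, and above all its hospitalization odds ratio. Figures 1 and 2 do not involve access, but they are unadjusted and cannot stand in for it.

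**Working it through.** The SAP gives no event count, peritoneal share or access distribution, so there is no planned figure to reproduce. All inputs below are assumptions, used to show direction and range.

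**Inputs.** Peritoneal share of home starts *s* = 0.50, 0.80, 0.90, 0.95. Half of patients are hospitalized. Home start is 14.66% without and 6.43% with hospitalization, an odds ratio (OR) of 0.40. In 400,000 patients this gives (0.14662 + 0.06431)/2 × 400,000 ≈ 42,185 home starts.

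**Coding 1: peritoneal level dropped.** Events left = 1 − *s*. The standard error (SE) of a log OR is governed mainly by the home events, so the SE ratio ≈ √(1/(1 − *s*)).

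| *s* | Home events left | SE ratio by formula | Simulated SE of log hospitalization OR (0.011 without access) |
|---|---|---|---|
| 0.50 | 50% | 1.41 | 0.016 |
| 0.80 | 20% | 2.24 | 0.025 |
| 0.90 | 10% | 3.16 | 0.035 |
| 0.95 | 5% | 4.47 | 0.050 |

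**Coding 3: catheter versus other.** Let *c₁* and *c₀* be catheter use among hemodialysis patients with and without hospitalization, the same for home and in-center.

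- Catheter stratum: only home hemodialysis contributes home events, and the hospitalization OR is 0.40.
- Other stratum: OR = 0.40 × [*s* + (1 − *s*)(1 − *c₁*)] / [*s* + (1 − *s*)(1 − *c₀*)] × (1 − *c₀*)/(1 − *c₁*).
- With *c₁* = 0.85, *c₀* = 0.60, *s* = 0.50: 0.40 × 0.575/0.700 × 0.40/0.15 = 0.88.
- With the same gradient and *s* = 0.95: 0.40 × 0.9575/0.970 × 0.40/0.15 = 1.05.

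The logit fits one common OR across the two strata. As *s* rises, nearly all home events fall in the other stratum, which then dominates. Fitting the logit to the expected cell counts gives:

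| Catheter use, hospitalized versus not | *s* = 0.50 | 0.80 | 0.90 | 0.95 |
|---|---|---|---|---|
| 85% versus 60% | 0.62 | 0.83 | 0.94 | 1.00 |
| 80% versus 70% | 0.48 | 0.54 | 0.57 | 0.58 |
| 80% versus 80% | 0.40 | 0.40 | 0.40 | 0.40 |

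A simulation of the first row gave 0.62, 0.83, 0.93 and 0.99. An assumed season OR of 0.90 kept its value under collapsed coding, because access was not made to vary by season.

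**A second set of assumptions for codings 1 and 2.** Catheter use was set at 90% versus 70% among in-center patients and 50% among home hemodialysis patients whatever their hospitalization, with *s* = 0.80 or 0.95, a true hospitalization OR of 0.40 and a winter OR of 0.90.

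- Access omitted: hospitalization OR 0.39 to 0.41, winter 0.89 to 0.92. The truth is recovered.
- Peritoneal level dropped: hospitalization OR 0.51 to 0.53, with the SE about 2.3 times (*s* = 0.80) or 4.6 to 4.7 times (*s* = 0.95) larger. Winter scattered over 0.84 to 0.93.
- Peritoneal access imputed as vascular: hospitalization OR 0.52 to 0.54, winter 0.89 to 0.92.

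The shift under codings 1 and 2 depends on catheter use differing between home and in-center hemodialysis patients. Where the hospitalization gradient is the same in both, as in the first set of inputs, the OR stays at 0.40 under both codings, and the damage in coding 1 is to precision and scope only.

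**The case against.** The strongest reply is that the mechanism depends on coding the SAP does not show. It does not name peritoneal dialysis or the source of the access variable, and the levels may be set out elsewhere. That is fair as far as the missing levels go. It does not touch the stated choice, which puts access into the at-start model whatever its levels.

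Second, every effect size is assumed. This stands. A large shift toward 1 occurs only under collapsed coding with a steep catheter gradient. The shifts under the other two codings need a further assumption about home hemodialysis patients. The 4.5-fold loss of precision needs a 95% peritoneal share.

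Third, season comes first in the SAP title, and no season bias has been demonstrated. This also stands. For season, the harm shown is lost precision when a peritoneal level is dropped. Hospitalization is, however, an exposure in its own right in A(b) and is also in the title.

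Fourth, the same-moment argument reaches only one of five logits and its interaction version. Perfect prediction would probably be noticed when the model is fitted. Both are true, but the collapsed coding would give no such warning.

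Finally, access among hemodialysis patients reflects preparation for dialysis, a plausible confounder of hospital start and home uptake. Removing access loses that adjustment, so reporting the model both ways is a possible alternative. The cost is real. It does not justify an adjusted at-start estimate that exists only conditional on a consequence of its outcome.

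**Conclusion.** The concern holds. As written, the at-start logit and its interaction version adjust for a variable that modality itself determines in peritoneal patients, and no planned adjusted analysis omits it.

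The direction is clear: loss of precision and a narrower comparison if a peritoneal level is dropped, and attenuation of the hospitalization odds ratio if levels are collapsed and catheter use is higher after hospitalization. The size is uncertain, ranging from no change in the odds ratio to complete loss of an assumed 0.40, because coding, peritoneal share and catheter gradient are all unstated. Nothing here shows bias in the season odds ratio. The models for months 3 to 12 and the Cox model are not wrong on this ground, since access may be a confounder or a mediator there. The change should be made before analysis, with medium confidence in how much it will matter.

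**What to change.** 1. In Regressions A, except access type from the covariates of the logit for home dialysis at start, and carry the same exception into that model's interaction version under C.
2. In item 4(a)(vii), state the access levels and how patients without vascular access are coded. In item 5, state that access is not imputed for patients to whom vascular access does not apply.
3. Optionally, add under D a sensitivity analysis without access for the month 3 to 12 logits and the Cox model, and report both sets of results.

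The cost is one covariate removed from one logit and its interaction version, a sentence or so on coding and, if wanted, one extra run. No new data are needed. The drawback is weaker adjustment for dialysis preparation in the at-start model, where the indicator for prior nephrologist care in item 4(a)(viii) remains but is coarse.

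### Ordinal logit is the only imputation model named, although several covariates have no order; the imputation list also omits season and every outcome after dialysis start

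*SAP*

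**What the plan says.** Item 5 of the SAP (under Cohort construction) imputes missing characteristics by chained equations with ordinal logit, using 10 imputations combined by Rubin's rules. The reason given is: "We use ordinal logit because all variables (including continuous ones) will be modeled as categorical variables". No other imputation model is named and no variable is exempted.

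The covariates to be imputed are those of item 4. Besides race and ESRD Network they include "Employment status", "Type of dialysis access at the start of dialysis" and "Primary reason for ESRD".

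Item 5a fixes the content of the imputation model: "Variables used for imputation: Covariates as above, type of dialysis at start, whether the patient had an acute cardiac/infectious-respiratory, or other hospitalization" in the 14 days around dialysis start. The item 4 covariates bring in calendar year (4d) but not season.

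The Regressions section uses the imputed data throughout. Season and hospitalization (with its type) are the exposures in A and B, and C interacts them. The logit outcomes are given as "Outcome: home dialysis at start, months 3, 6, 9, 12", and the Cox model analyses time to home dialysis. The only planned check on the imputation is the complete-case analysis in D(a).

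**The concern.** The stated reason does not support the method. Ordinal logit needs ordered categories and assumes that each predictor acts with the same slope at every cut-point. For a nominal variable the cut-points exist only because someone numbered the levels, and a different numbering gives a different model. The SAP fixes no numbering, so two analysts who follow it exactly can obtain different imputations and different adjusted estimates from the same data. If the covariate confounds hospitalization and home dialysis, poorly imputed values also leave part of that confounding unadjusted.

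The second, lesser problem is what 5a leaves out. An imputation model should contain the variables of the analysis model, including its outcome. List 5a does this for home dialysis at start, apart from season. It does not for the month 3 to 12 logits, the Cox model or the season-by-hospitalization interaction. Imputing a covariate without the outcome weakens its association with that outcome, and so weakens the adjustment.

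**Working it through.** **No SAP figure to reproduce.** The SAP gives no sample size, effect size, missing fraction or category levels. All numerical inputs below are assumptions that illustrate the mechanism.

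**Why numbering matters.** For a covariate C with levels 1 to K and predictors x:

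- Ordinal logit: logit P(C ≤ j | x) = κ_j − x′β, with one β for all j. Renumbering changes the sets {C ≤ j} and so changes the model. Only a complete reversal leaves it the same, with the sign of β flipped. Four levels therefore give 4!/2 = 12 distinct models.
- Multinomial logit: log[P(C = k | x)/P(C = 1 | x)] = α_k + x′γ_k. Each level has its own slopes, so relabelling changes nothing.
- With two levels, ordinal logit is ordinary logit. Binary covariates, and continuous ones cut into ordered bands, are therefore handled properly.

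**Calculation 1 (simulation, n = 100,000).** Assumed inputs: C has four levels with probabilities 0.45, 0.25, 0.20, 0.10. Its log-odds effects are 0, 1.2, −0.6, 0.8 on hospitalization (H) and 0, −1.2, 0.7, −0.8 on home dialysis. C is missing completely at random and is imputed from H and start modality. Five imputations were made without parameter draws. The analysis is a logit on H, winter and C. Hospitalization log odds ratio:

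| | Full data | 10% missing | 20% | 30% |
|---|---|---|---|---|
| Start, ordinal, 12 numberings | −0.66 | −0.73 to −0.66 | −0.80 to −0.67 | −0.86 to −0.67 |
| Start, multinomial | −0.66 | −0.66 | −0.67 | −0.66 |
| Month 12, ordinal, 12 numberings | −0.63 | −0.72 to −0.66 | −0.79 to −0.69 | −0.86 to −0.71 |
| Month 12, multinomial, 5a predictors | −0.63 | −0.66 | −0.68 | −0.70 |
| Month 12, multinomial, plus season and month-12 outcome | −0.63 | −0.63 | −0.63 | −0.63 |

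The imputed probabilities show the cause. Among hospitalized home starters at 10% missing, the true share in the second level is 0.143, but ordinal logit gives 0.162 to 0.283. The true share in the third is 0.294, against 0.209 to 0.279. No numbering reaches either true value. The winter coefficient for the start outcome was −0.064 to −0.074 across numberings and missing rates, against −0.077 in full data.

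**Calculation 2 (large-sample, no Monte Carlo error).** The imputation model was fitted to the observed part of an assumed joint distribution, the missing part filled in, and the outcome logit refitted. Full-data hospitalization log odds ratio −0.80, start outcome, 5a predictors. Shift over the 12 numberings:

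| Confounder | 2% missing | 10% | 30% |
|---|---|---|---|
| Strong (coefficients up to 1.0) | −0.000 to −0.019 | −0.002 to −0.091, median −0.060 | −0.007 to −0.229, median −0.155 |
| Mild (up to 0.4) | at most −0.003 | at most −0.013 | at most −0.035 |

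Multinomial logit with the same predictors: 0.000 throughout. As odds ratios for the strong case, exp(−0.80) = 0.45 becomes at worst exp(−0.891) = 0.41 at 10% and exp(−1.029) = 0.36 at 30%. If the covariate's effects are evenly graded and it is numbered in that order, the shift at 10% is −0.0003; other numberings give up to −0.028.

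The omissions in 5a alone (multinomial imputation, month-12 logit) shift the hospitalization estimate by −0.003 to −0.017 at 10% and −0.008 to −0.050 at 30%. The effect is near zero for the start outcome. The winter main effect moves by at most 0.017 and the winter-by-hospitalization term by at most 0.023.

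**Interval coverage.** A Monte Carlo check of the start logit (assumed N = 20,000, 40 runs, 10 imputations, Rubin's rules, 10% missing, one numbering) gave 95% interval coverage of 60% for ordinal and 97% for multinomial with the strong confounder, and 93% and 97% with the mild one. With 40 runs, the standard error of the 60% is √(0.6 × 0.4/40) = 0.08. The shifts in this check, −0.091 and −0.013, equal the extremes of the 10% column above, so it shows the least favourable numbering.

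**A third large-sample check** with other inputs gave −0.002 to −0.056 at 10% and −0.006 to −0.144 at 30% for a strong confounder, and at most −0.024 for a mild one.

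**The case against.** The strongest reply concerns size. The SAP does not say which covariates are incomplete or by how much. Item 1b requires a medical evidence form for every patient, which makes heavy missingness in form-based items less likely. At 2% missing, or with mild confounding, the shift is trivial. The 60% coverage combines a strong confounder, the worst numbering and an assumed sample size. Employment and access type could be coded in two levels or in a meaningful order, and ordinal logit would then be acceptable or nearly so. All this stands as a limit on the size. It does not help race, cause of ESRD or Network, nor does it make the stated rationale correct.

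The complete-case analysis is also a better safeguard than it may seem. Its coefficients are valid when values are missing completely at random, and also when missingness depends on the model's exposures and covariates but not on the outcome given these. It could therefore reveal a large artefact. It would not repair the main analysis.

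On 5a, the measured gain from adding season is small. The size of the outcome omission varies with the inputs (at 10% missing, at most 0.017 in one calculation and about 0.03 in another), and the Cox model was not simulated. That is why this part is secondary.

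**Conclusion.** The point holds and should be fixed. Applied as written to an unordered covariate with missing values, item 5 makes the imputations depend on arbitrary numbering and can bias the adjusted hospitalization estimates. That follows from the form of the model and does not rest on assumed inputs.

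The size does. It is negligible when little is missing or confounding is weak, and reaches roughly 0.06 to 0.09 on the log-odds scale at 10% missing, and 0.14 to 0.23 at 30%, for a strong confounder under the least favourable numbering in the three calculations. In these examples the bias exaggerates the hospitalization effect, because the levels with more hospitalization also have less home dialysis; other confounding patterns could reverse it. Every quantified case assumes a single incomplete four-level covariate, missing completely at random.

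The omissions from 5a are a real but smaller fault, affecting mainly the month 3 to 12 logits and, in principle, the Cox model. No material distortion of the season main effect was found.

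**What to change.** In item 5, state that unordered covariates (race, cause of ESRD, Network, and employment and access type unless coded as binary or with a defined order) are imputed by multinomial logit, and keep ordinal logit for ordered ones. This costs one line of text. Sparse levels, for example of Network or cause of ESRD, may need collapsing for the model to fit.

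In 5a, add season and its interaction with hospitalization. For the Cox model, add the home-dialysis event indicator and the Nelson-Aalen cumulative hazard. For each month 3 to 12 logit, include that month's outcome in an imputation run restricted to the patients in that analysis, so that modality is not imputed where death or transplant leaves it undefined. Item 3a(i) already creates an indicator of being alive at each of these months. The cost is a separate imputation run per outcome and longer computing time; no new data are needed.

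### Figure 1C's log-rank test is not a valid test of the seasonal difference in the figure's title, and no other planned test asks whether hospital starts vary by season

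*SAP*

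**What the plan says.** All of this is in the SAP under Planned Analyses, unless noted.

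- **Figure 1, title:** "Unadjusted seasonal differences in home dialysis and # of patients starting with a hospitalization".
- **Figure 1, panels:** A is specified as "Y axis: # of in-center patients, X axis: time; series: show patients who start with a hospitalization", with patients who start without one as the second series. B has the same layout for home patients. Season is not a series in either panel.
- **Figure 1, item C:** "Compute log rank test (p-value"), and nothing more.
- **Figure 2:** Kaplan-Meier curves of time to home dialysis, with censoring reasons and a one-year limit, by season (A) and "By whether patients start with and without a hospitalization" (B). Its item C reads "Compute log rank test (p-value) for A & B".
- **Figure 3:** "Kaplan-Meier survival curves, censoring for loss to follow-up", for mortality, by season.
- **Table 2:** "Descriptive statistics (frequencies and percentages) of each hospitalization type by season of year", followed by "Compute the ratio in frequency between winter and summer".
- **Regressions A and B:** the outcomes are home dialysis at five time points and time to home dialysis. Season and hospitalization are both exposures. The subgroup analyses repeat A and B with the two exposures interacted.
- **Cohort construction, item 3c:** hospitalization in the 14 days before dialysis start is a listed outcome. Starting dialysis in hospital is also half of the study title.

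**The concern.** A log-rank test needs an event, a time origin, a risk set and groups. Figures 2 and 3 supply these and Figure 1 does not, so this is not just a terse style used throughout the SAP. The analyst would have to invent the test, and the p-value would appear under a title that promises a seasonal comparison.

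The stake is outcome 3c. Seasonal differences in home dialysis are tested in Figure 2A, the logits and the Cox model. Seasonal differences in hospital start are not tested anywhere: hospitalization enters the regressions only as an exposure, and Table 2 is descriptive. Figure 1C is the only p-value placed under a heading about season and hospital starts. If it is significant because of a long-term trend, a reader could take the trend for a season effect.

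**Working it through.** The SAP states no sample size, power or significance level, so there is no figure of its own to reproduce. The check is a reading of the text, with a simulation as illustration.

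**Step 1. Possible readings of item C**

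| Reading of time | What the log-rank compares | Is it a test of season? |
|---|---|---|
| Calendar date of start, ten years | Start-date distributions of hospital and non-hospital starters | Hardly: seasonal swings largely cancel over ten years, while trend accumulates |
| Time since dialysis start | Hospital against non-hospital starters | No: this is the contrast of Figure 2B, already tested in 2C |
| Month within the year | Within-year start distributions of the two series | Sensitive to season, but dependent on where the year is cut |

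A log-rank by season of time to home dialysis would test season, but that is Figure 2A.

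**Step 2. Illustration of the calendar-time reading**

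Assumed, not in the SAP: 50,000, 200,000 or 400,000 starts; hospital share 30% or 50%; 120 months with starts proportional to days; winter share raised and summer share lowered by half the stated difference; drift linear, stated as the total change over ten years; every start an event; 5% level; 4,000 runs per cell. In-center and home patients are pooled, so neither panel is modelled separately.

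| Scenario | Log-rank rejects | Four-season chi-square (3 df) rejects |
|---|---|---|
| No season effect, no drift | 4.1-5.4% | 4.3-5.5% |
| 2-point seasonal difference | 5.9-10.4% | 76.1-100% |
| 4-point seasonal difference | 6.8-27.4% | 100% |
| No season effect, 2-point drift | 61.6-100% | 4.8-8.5% |

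**Step 3. Folded year**

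A separate run assumed 100,000 starts, a 50% share and a winter:summer ratio of hospital starts of 1.2. The log-rank rejected in 96% of runs with the year cut at December, 25% at January and 21% at July. The data were the same and only the origin changed.

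**Step 4. What the replacement test must handle**

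With no season effect and a 5-point drift, the plain chi-square rejects in 7.0-34.6% of runs. The reason is arithmetic. The drift is 5/10 = 0.5 points per year. Winter as the SAP defines it is centred in mid-January and fall (taken as September-November) in mid-October, 9 months later, so fall differs from winter by 0.5 x 9/12 = 0.375 points from drift alone. Indicators for the SAP's December-to-November years do not remove this, because the drift within each year remains aligned with season. Stratifying by year still rejected about 14-35% at 200,000-400,000 starts. A continuous calendar-time term models the drift directly.

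**Step 5. Table 2**

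With winter as December-February (item 2b) and summer taken as June-August, the window 12/1/2007 to 11/30/2017 has 903 winter and 920 summer days. If daily hospital starts did not vary by season, the count ratio would be 903/920 = 0.98.

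**The case against.** The strongest reply is that this is one p-value on an unadjusted figure. Item 2 of Cohort construction builds season and year from the date of first dialysis, so calendar time is the natural axis and season would be visible along it. That stands: the plots are sound and need only a label. It does not make the log-rank a test of season.

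A second reply is that the folded-year reading, cut at December as item 2b cuts its years, does detect seasonality. That also stands as a fact, and it would be wrong to say that every reading is blind to season. But the SAP does not specify this reading, and a result that moves from 96% to 21% rejection with the choice of origin is not a usable test.

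Third, the simulation pools the two panels and uses assumed sizes. This is correct. The rates show the direction of the problem and are not the size of an error in this study.

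A reader might also infer that the Table 2 ratio is wrong. The document does not support that. The text fixes no formula, a ratio of counts is a legitimate description of how many hospital starts fall in each season, its departure from 1 through day counts is about 2%, and the percentages in the same table let a reader form the ratio of proportions. If winter brings more starts per day, a count ratio describes that correctly.

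**Conclusion.** The point holds, and the textual defect is certain. Item C of Figure 1 lacks the elements of a log-rank test, and none of the readings above makes it a valid test of the seasonal difference in the title. Outcome 3c by season has no other planned test. Its practical size cannot be fixed from the SAP, because the number of starts, the hospital share and any trend are not given.

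It would go too far to infer that the seasonal results on home dialysis are compromised: Figures 2 and 3, the logits and the Cox model do not use this test. Table 2 is a secondary wording matter. The change should be made before analysis, but it is limited to one test and one label.

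**What to change.** 1. Delete the log-rank line from Figure 1 and label the X axis of both panels as calendar month or season-year of dialysis start.
2. Add one test of hospital start (any, and by type) across the four seasons. A suitable form is a 3-df Wald test from a logit of hospital start on season, with robust standard errors and a continuous calendar-time term. The yearly indicators of item 4d alone would leave within-year drift confounded with season.
3. In Table 2, state whether the winter/summer ratio is of counts or of within-season proportions, preferably the latter.

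The cost is SAP wording and one extra analysis on variables already planned. No new data are needed.
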